2. OBJECTIVES AND ENDPOINTS

Primary objective:

To determine the frequency and timing of folate deficiency in patients with solid tumors harboring molecular alterations such as germline and somatic mutations in *BRCA1* and *BRCA2* genes, other genes in Homologous DNA Recombination Repair (HRR) pathway, genomic stability as determined by Homologous Recombination Deficiency (HRD) assay, etc., who are treated with olaparib.

Secondary objectives:

To evaluate the effect of folic acid supplementation on serum folate, hemoglobin level, transfusion needs/number of transfusions, and need for olaparib treatment interruption, dose reduction and drug discontinuation.

To assess response rate (RR) to olaparib as it relates to serum folate level and folic acid supplementation.

Clinical Study Protocol - 6
Olaparib - ESR-18-13807

To assess progression-free survival (PFS) as it relates to serum folate level and folic acid supplementation.

Exploratory objectives:

To elucidate the mechanism of folate deficiency in patients treated with olaparib including possible interaction with germline *BRCA1* and *BRCA2* mutations via testing for folate receptors using immunohistochemistry on available paraffin embedded tumor samples from enrolled patients.

Primary endpoint:

The primary binary endpoint of the study is the percentage of patients who develop drug-induced folate deficiency, defined as serum folate level <7 ng/mL, within three months from start of olaparib therapy.

Secondary endpoints:

To assess the impact of folic acid supplementation on anemia, need for transfusion, and olaparib treatment interruption, dose reduction and drug discontinuation as compared to those who did not receive/require folic acid supplementation

To determine tumor response rate (RR), using treating physician assessment, on olaparib therapy in patients who develop folate deficiency and receive folic acid supplementation as compared to those who do not receive/require folic acid supplementation. Will also compare RR to historical controls (patients with solid tumors treated with olaparib or other approved agents on clinical trials).

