To determine progression-free survival (PFS), using treating physician assessment based on olaparib therapy in patients who develop folate deficiency and receive folic acid supplementation as compared to those who do not receive/require folic acid supplementation. Will also compare PFS to historical controls (patients with solid tumors treated with olaparib or other approved agents on clinical trials) using published data.

Exploratory Endpoints:

To evaluate association between:

- *BRCA 1*, *BRCA 2*, and other HRR gene status (germline mutation carrier vs non-carrier) and the intensity of folate receptor alpha expression in the tumor ($<50\%$ or $>50\%$)
- *BRCA 1*, *BRCA 2*, and other HRR gene status (germline mutation carrier vs non-carrier) and nadir serum folate level during olaparib treatment

Clinical Study Protocol - 6
Olaparib - ESR-18-13807

- *BRCA 1*, *BRCA 2*, and other HRR gene status (germline mutation carrier vs non-carrier) and tumor response in patients receiving folate supplementation as compared to patients not receiving folate supplementation and historical controls
- Folate deficiency and expression of folate receptors in patients' tumor samples

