4.1 Inclusion criteria

Patients are eligible to be included in the study only if all of the following inclusion criteria and none of the exclusion criteria apply:

Informed consent

1. Capable of providing a signed informed consent which includes compliance with the requirements and restrictions listed in the informed consent form (ICF) and in this protocol.
2. Provision of signed and dated, written informed consent form prior to any mandatory study specific procedures, sampling, and analyses.
3. For inclusion in the optional biomarker research, patients must fulfil the following criteria:
 - Provision of informed consent for biomarker research prior to collection of sample

If a patient declines to participate in the optional biomarker research, there will be no penalty or loss of benefit to the patient. The patient will not be excluded from other aspects of the study.

Age

4. Patient must be ≥ 18 years of age inclusive, at the time of signing the informed consent form.

Type of patient and disease characteristics

Patients with solid tumors harboring molecular alterations which are likely to respond olaparib, such as germline and somatic mutations in *BRCA1* and *BRCA2* genes, other genes in Homologous DNA Recombination Repair (HRR) pathway, genomic stability as determined by Homologous Recombination Deficiency (HRD) assay, etc. Olaparib must be recommended to these patients by their treating physician.

Clinical Study Protocol - 6
Olaparib - ESR-18-13807

6. Patients must have normal organ and bone marrow function measured within 28 days prior to administration of study treatment as defined below:
- Haemoglobin ≥ 10 g/dL with no blood transfusion in the past 28 days
 - Absolute neutrophil count (ANC) $\geq 1.5 \times 10^9/L$
 - Platelet count $\geq 100 \times 10^9/L$
 - Total bilirubin ≤ 1.5 x institutional upper limit of normal (ULN)
 - Aspartate aminotransferase (AST) (Serum Glutamic Oxaloacetic Transaminase (SGOT)) / Alanine aminotransferase (ALT) (Serum Glutamic Pyruvate Transaminase (SGPT)) ≤ 2.5 x institutional upper limit of normal unless liver metastases are present in which case they must be ≤ 5 x ULN
 - Patients must have creatinine clearance estimated of ≥ 51 mL/min using the Cockcroft-Gault equation or based on a 24 hour urine test :

$$\text{Estimated creatinine clearance} = \frac{(140 - \text{age [years]}) \times \text{weight (kg)}}{\text{serum creatinine (mg/dL)}} \times F^a$$

^a where F=0.85 for females.

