7.5 Biomarkers

Optional samples for biomarker research that should be collected from patients in the study where possible are the following:

- Existing paraffin embedded tissue samples from patients will be collected for assessment of folate receptors via immunohistochemical staining as according to the previously stated Exploratory Objective/Endpoint.

Unless otherwise specified in the protocol, biomarker data will not be routinely reported to sites unless specifically requested. Frequently, biomarker data are generated retrospectively towards the end of the study. Any sample material remaining after completion of analyses to fulfil the study objectives may be used for optional exploratory research to develop methods, assays, prognostics, and/or companion diagnostics related to cancer, disease process, pathways associated with disease state, PARP, and or mechanism of action of olaparib.

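### The folate receptor alpha endpoint splits expression strictly below or above 50%, which leaves a reading of exactly 50% in no class and discards information in a small optional tissue subset

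*Combined protocol and SAP*

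**What the plan says.** Section 2 (Objectives and Endpoints) sets an exploratory objective of explaining how folate deficiency arises under olaparib, including a possible interaction with germline *BRCA1/2* mutations, "via testing for folate receptors using immunohistochemistry on available paraffin embedded tumor samples from enrolled patients". The first exploratory endpoint relates gene status, given as "other HRR gene status (germline mutation carrier vs non-carrier", to "the intensity of folate receptor alpha expression in the tumor". The parenthesis that follows gives two classes, strictly below 50% and strictly above 50%. A separate bullet in the same list covers "Folate deficiency and expression of folate receptors in patients' tumor samples" and has no cut. Another relates carrier status to nadir serum folate, also without a cut.

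On the tissue, Section 7.5 (Biomarkers) says "Existing paraffin embedded tissue samples from patients will be collected for assessment of folate receptors via immunohistochemical staining" and introduces this with "Optional samples for biomarker research that should be collected from patients in the study where possible are the following". Section 4.1 lets patients refuse: "If a patient declines to participate in the optional biomarker research, there will be no penalty or loss of benefit to the patient".

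Section 8.2 proposes 75 patients, and Section 8.5 foresees a review of accrual after the first 30. Section 8.4.1 leaves the exploratory analysis to the SAP. The supplied text contains no such analysis, no scoring system for the stain and no reason for choosing 50%.

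**The concern.** There are two separate faults in one short parenthesis.

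The first is a gap. With two strict inequalities, a reading of exactly 50% has no class. If readings are made by eye in steps of 5 or 10 points (an assumption, since no method is stated), 50% is a value that can be expected to occur. If the rule is settled only after slides are read, those tumours can be dropped or placed on either side with the carrier comparison already visible.

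The second is loss of information. A graded measure reduced to two classes treats a tumour just above the cut and one far above it as the same. That matters most when there are few samples, and here the number is limited by enrolment, consent and the availability of archival blocks. At stake is the one planned comparison that links germline status to receptor expression: a real association becomes easier to miss, and a null result harder to interpret.

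**Working it through.** **Ceiling on the tissue subset.** The plan states no sample size or power for this endpoint, so the only figure to reproduce is the enrolment total.
- Inputs from Section 8.2: null 50%, expected 66%, one-sided 0.05, 80% power, 20% attrition.
- An exact binomial test with 60 patients that rejects at 37 or more has one-sided error 0.046 and power 0.802, so 60 is reproduced.
- 60 / (1 − 0.20) = 75, also reproduced.
- Tissue is optional, so the subset is at most 75. If accrual ended at the Section 8.5 review, it would be at most 30.

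**Is the gap real?** The two classes are below 50% and above 50%, and their union omits 50%. A lost inclusive sign cannot be wholly excluded, because the text was read from PDF. However, inclusive signs survive elsewhere in the same document, for example in the haemoglobin criterion of Section 4.1 and in Table 8. No other section assigns the value.

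**Information kept by a two-class split.** Assume a roughly normal score (the documents give no distribution). For a shift between two groups, the efficiency of the split relative to the full score is

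E(q) = φ(z_q)² / [q(1 − q)],

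where q is the share of tumours below the cut, z_q the corresponding normal quantile and φ the normal density.

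| Share below cut | φ(z_q)² | q(1 − q) | E |
|---|---|---|---|
| 0.50 | 0.1592 | 0.25 | 0.637 |
| 0.70 | 0.1209 | 0.21 | 0.576 |
| 0.80 | 0.0784 | 0.16 | 0.490 |
| 0.90 | 0.0308 | 0.09 | 0.342 |

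E is symmetric in q, so a 20/80 split gives 0.490 whichever side holds the larger share.

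**Against the proposed test.** These ratios compare the split with a fully efficient normal-theory analysis. Under normality the Wilcoxon rank-sum test has efficiency 3/π = 0.955. Relative to Wilcoxon, the split therefore keeps 0.637 / 0.955 = 0.667 at the median and 0.490 / 0.955 = 0.513 at 20/80.

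**What this means for power (illustration).** Assume N tissue samples from 20 to 75, a carrier share c of 30% or 50%, a unit-variance normal score and a two-sided 0.05 test. Take the shift that gives 80% power on the full score:

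d = (1.960 + 0.842) × √[1/(Nc) + 1/(N(1 − c))].

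For N = 75 and c = 0.5, d = 2.802 × √(4/75) = 0.65. With the cut at the overall median, 37.3% of non-carriers and 62.7% of carriers lie above it, and the two-proportion comparison has power 0.597. Over all the assumed combinations, power is about 52% to 60% with a median cut and about 38% to 55% when 80% of tumours fall below the cut.

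**The case against.** The strongest reply is that the analysis is expressly left to the SAP, which could place 50% in a class and add an analysis of the graded score. That is possible. However, the two classes are written into the endpoint definition in Section 2, so an SAP that follows the protocol inherits both the gap and the split. The reply limits the severity but does not remove the point.

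It is also fair to say that the size of the loss is hypothetical. Nothing is known about the distribution or about where 50% falls in it. If tumours form two clusters well apart on either side of the cut, class membership carries most of the information and little is lost. This stands, and the figures above are conditional for that reason.

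Three stronger readings are tempting, and the documents support none of them.
- A reader might infer that this is the trial's only direct test of mechanism. It is not: the bullet on "Folate deficiency and expression of folate receptors in patients' tumor samples" also addresses it, ties receptor expression to the folate outcome itself and has no cut.
- A reader might infer that the laboratory will hold a percentage for each tumour anyway. No scoring method is stated, and readers could record only a class or an intensity grade.
- A reader might turn the efficiencies into an effective number of patients, such as 75 × 0.637 = 48 or 75 × 0.490 = 37. That would require a normal score, a known cut position and tissue from all 75 patients, none of which the documents give.

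Finally, the endpoint is exploratory in a study that calls itself a pilot, and no power is claimed for it. This is correct and keeps the point minor.

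**Conclusion.** The point holds as a minor, inexpensive improvement. The gap at exactly 50% follows from the wording alone and needs no assumption beyond the printed signs being correct. The loss of information is certain in direction for a graded score but uncertain in size. Under assumed normality the split keeps about 64% at best and about 49% at 20/80, with less lost if readings cluster away from the cut. The subset affected is optional tissue from at most 75 patients, and the comparison affected is the only planned one between germline carrier status and folate receptor alpha expression. The other mechanism endpoints carry no such cut, and the primary result on folate deficiency does not depend on this one.

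**What to change.** Amend Section 2 and write the matching analysis into the SAP before any slides are read:
- State what the percentage measures. The endpoint speaks of intensity but gives a percentage, which could mean strength of staining or share of stained tumour cells. Name the scoring scale.
- Record the score as read for every tumour.
- Make the comparison of the recorded score by carrier status the main exploratory analysis, by Wilcoxon rank-sum test (which does not need normality) or by regression.
- Keep the two classes as a descriptive table, with the cut closed as below 50% versus 50% or more.

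No extra patients or tissue are needed. The cost is a change of wording, a requirement that readers record the score and not only a class, and slightly more explanation when the result is reported.

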3. STUDY DESIGN

3.1 Overall design

This is a pilot, multi-center study evaluating the prevalence and timing of folate deficiency in patients with advanced solid tumors who are eligible to receive olaparib.

If patients develop folate deficiency concomitantly with a Hgb less than 12.0 g/dl (grade 1), they will then be randomized to receive either a placebo or folate supplementation.

All randomized patients who develop a Hgb less than 10 g/dl (grade 2) concomitantly with folate deficiency will receive folic acid supplementation irrespective of their prior randomization. If such patients were originally randomized to receive folic acid and continue to have a Hgb less than 10 g/dl and folate deficiency despite folate supplementation, folic acid dose will be increased to 2 mg daily or higher at the discretion of the investigator.

Patients will continue with olaparib until objective disease progression (determined by treating physician assessment) as long as in the Investigator's opinion they are benefiting from treatment and they do not meet any other discontinuation criteria.

For an overview of the study design see Figure 1, Section 1.3. For details on treatments given during the study, see Section 5.1 Treatments Administered.

For details on what is included in the efficacy and safety endpoints, see Section 2 Objectives and Endpoints.

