1. PROTOCOL SUMMARY

1.1 Schedule of Activities (SoA)

1. Participants will be screened for eligibility with medical history, physical exam, prior treatment, history of anemia and blood tests including baseline CBC, reticulocyte count, ferritin, B-12 and serum folate level
2. If inclusion criteria are met and after signing a consent form, participants will start olaparib 300 mg twice daily, commercially approved
3. Assessment of CBC/serum folate will occur every 2 weeks for the first 3 months and then monthly for a total of 6 months from the time of enrollment onto study therapy. If the patient develops folate deficiency and requires folate replacement, CBC/serum folate and reticulocyte count will occur every 2 weeks for 12 months.
4. One-time measurement of serum folate to occur one month after completion or discontinuation of therapy with olaparib
5. If folate deficiency is identified (defined as any level below normal) at any time point, the following parameters will be assessed in 2 weeks or at the next visit/assessment point: a repeat CBC/serum folate level along with B-12, LDH, reticulocyte count, methylmalonic acid, and homocysteine. These labs (CBC/serum folate level, B-12, LDH, reticulocyte count, methylmalonic acid, and homocysteine) need to be drawn once- 2 weeks after initial folate deficiency is identified for confirmation purposes and to rule out co-existing B-12 deficiency or other causes of anemia.
6. Once folate deficiency is confirmed in the setting of hemoglobin (Hgb) less than 12 g/dl but above 10.0 g/dl, patients will be randomized to folate supplementation or placebo. At that point, assessment of CBC/reticulocyte count and folate levels will continue every 2 weeks.
7. If Hgb is above 12.0 g/dl and no folate deficiency is identified, patients will not be randomized. Assessment of CBC/serum folate will continue every 2 weeks for the first 3 months and then monthly for a total of 6 months from the time of enrollment onto the study.
8. If folate deficiency is identified in setting of Hgb less than 10.0 g/dl, patients will not be randomized but will receive folic acid supplementation at 1 mg daily. These patients will have weekly assessments of CBC/reticulocyte count and folate levels until Hgb improves to a level above 10.0 g/dl. At that point, assessment of CBC/reticulocyte count and folate levels will change back to every 2 weeks. However, folic acid replacement will continue as initiated.

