7.4.4 Management of adverse events Dose Reductions

Any toxicity observed during the course of the study could be managed by interruption of the dose of study treatment or dose reductions. Repeat dose interruptions are allowed as required, for a maximum of 4 weeks on each occasion. If the interruption is any longer, the study team must be informed. Study treatment can be dose reduced to 250 mg twice daily as a first step and to 200

Clinical Study Protocol - 6
Olaparib - ESR-18-13807

mg twice daily as a second step. If the reduced dose of 200 mg twice daily is not tolerable, no further dose reduction is allowed, and study treatment should be discontinued.

Once dose is reduced, escalation is not permitted (except following concomitant treatment with CYP3A4 inhibitors – see Section 6.5

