7.4.4.1 Management of haematological toxicity

7.4.4.2 Management of anaemia

Table 8 Management of anaemia

Haemoglobin	Action to be taken
Hgb < 10 but ≥ 8 g/dl (CTCAE Grade 2)	
First occurrence: Give appropriate supportive treatment and investigate causality. Investigator judgement to continue olaparib with supportive treatment (e.g., transfusion) or interrupt dose for a maximum of 4 weeks. Study treatment can be restarted if Hb has recovered to > 9g/dl.
 
Subsequent occurrences: If Hgb < 10 but ≥ 9 g/dl investigator judgement to continue olaparib with supportive treatment (e.g., transfusion) or dose interrupt (for max of 4 weeks) and upon recovery dose reduction may be considered (to 250 mg twice daily as a first step and to 200 mg twice daily as a second step). If Hgb < 9 but ≥ 8 g/dl, dose interrupt (for max of 4 weeks) until Hb ≥ 9 g/dl and upon recovery dose reduction may be considered (to 250 mg twice daily as a first step and to 200 mg twice daily as a second step).

Hgb < 8 g/dl (CTCAE Grade 3)	
Give appropriate supportive treatment (e.g., transfusion) and investigate causality. Interrupt olaparib for a maximum of 4 weeks until improved to Hgb ≥ 9 g/dl. Upon recovery dose reduce to 250 mg twice daily as a first step and to 200 mg twice daily as a second step in the case of repeat Hgb decrease.

Common treatable causes of anemia (e.g., iron, vitamin B12 or folate deficiencies and hypothyroidism) should be investigated and appropriately managed. In some cases management of anemia may require blood transfusions. For cases where patients develop prolonged haematological toxicity (≥2 week interruption/delay in study treatment due to CTC grade 3 (Hgb less than 8.0 g/dl) or worse anemia and/or development of blood transfusion dependence), refer to guidance later in this section for the management of this.

Clinical Study Protocol - 6
Olaparib - ESR-18-13807

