7.4.4.3 Management of neutropenia, leukopenia and thrombocytopenia

Table 9 Management of neutropenia, leukopenia and thrombocytopenia

Toxicity	Study treatment dose adjustment
CTCAE Grade 1-2	Investigator judgement to continue treatment or if dose interruption, this should be for a maximum of 4 weeks; appropriate supportive treatment and causality investigation
CTCAE Grade 3-4	Dose interruption until recovered to CTCAE gr 1 or better for a maximum of 4 weeks. If repeat CTCAE grade 3-4 occurrence, dose reduce olaparib to 250 mg twice daily as a first step and 200 mg twice daily as a second step

Adverse event of neutropenia and leukopenia should be managed as deemed appropriate by the investigator with close follow up and interruption of study drug if CTC grade 3 or worse neutropenia occurs.

Primary prophylaxis with Granulocyte colony-stimulating factor (G-CSF) is not recommended, however, if a patient develops febrile neutropenia, study treatment should be stopped and appropriate management including G-CSF should be given according to local hospital guidelines. Please note that G-CSF should not be used within at least 24 h (7 days for pegylated G-CSF) of the last dose of study treatment unless absolutely necessary.

Platelet transfusions, if indicated, should be done according to local hospital guidelines.

For cases where patients develop prolonged haematological toxicity (≥ 2 week interruption/delay in study treatment due to CTC grade 3 or worse), refer to guidance later in this section for the management of this.

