8.4 Statistical analyses

8.4.1 Efficacy analyses

Patients will be monitored for development of anemia and folate deficiency at scheduled time points throughout the course of the study, as described in Section 1.1. Patients who develop \leq G2 cytopenias and folate deficiency will be randomly assigned in a 1:1 ratio to receive folic acid supplementation 1 mg daily or no supplementation. Patients who develop G3 or higher cytopenias and folate deficiency will be started on folic acid supplementation, thus not included in the randomization. For patients who are randomized, we will assess the impact of folic acid supplementation on anemia, need for transfusion, and dose interruption, dose reduction and drug discontinuation of olaparib as compared to those who did not receive/require folic acid supplementation. Additionally, PFS and RR to olaparib will be compared amongst randomized patients relative to folic acid supplementation.

The statistical analysis will provide descriptive summaries as well as 95% confidence intervals for the primary endpoint of drug-induced folate deficiency in addition to response rate and other secondary endpoints. Kaplan-Meier methodology will be used to estimate the PFS curve and estimate of median PFS and corresponding 95% confidence interval will be provided. The significance of the observed percentage of folate-deficient cases will be assessed by statistical hypothesis test, as well as by multivariable analysis of the binary endpoint of folate deficiency adjusted by important covariates. Covariates will include age, race/ethnic group, previous therapy, Hgb prior to olaparib therapy, genetic testing result (*BRCA* carrier status). RR and PFS will be compared to historical controls as a descriptive comparison. Analyses will be reported on the entire combined cohort of patients with solid tumors and also separately for each cancer type. The statistical analysis of the exploratory endpoint will be specified in the SAP. Statistical analysis will be performed in the R Statistical software. No adjustment for multiplicity will be made.

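### Randomised controls start folic acid at the haemoglobin level where transfusion and olaparib changes for anaemia first appear, so these outcomes compare early with deferred supplementation

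*Combined protocol and SAP*

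**What the plan says.** Entry to the randomised part is set in Section 1.1, item 6: "Once folate deficiency is confirmed in the setting of hemoglobin (Hgb) less than 12 g/dl but above 10.0 g/dl, patients will be randomized" to folic acid or placebo, with blood counts every two weeks from then on.

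The switch is in Section 3.1: "All randomized patients who develop a Hgb less than 10 g/dl (grade 2) concomitantly with folate deficiency will receive folic acid supplementation irrespective" of arm. It needs both conditions at once, low Hgb and folate deficiency. Patients already on folic acid may have their dose raised.

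Table 8 in Section 7.4.4.2 is the only anaemia-specific action table. Its top row is "Hgb < 10 but ≥ 8 g/dl (CTCAE Grade 2", and it has no row for Hgb of 10 to 12 g/dl. At a first occurrence that row offers "Investigator judgement to continue olaparib with supportive treatment (e.g., transfusion" or interruption of olaparib; dose reduction follows at later occurrences.

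Section 8.4.1 takes these events as randomised outcomes: "For patients who are randomized, we will assess the impact of folic acid supplementation on anemia, need for transfusion, and dose interruption, dose reduction" and discontinuation. There and in Section 2, the comparator is people who did not get, or did not need, supplementation. Section 2 also lists serum folate and Hgb level, with no time window. Section 8.3 defines one population, anyone with at least one olaparib dose. No section says how a control who starts folic acid is to be analysed.

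Section 8.4.1 also draws the entry boundary differently. It randomises cytopenias up to grade 2 and adds: "Patients who develop G3 or higher cytopenias and folate deficiency will be started on folic acid supplementation, thus not included in the randomization".

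**The concern.** The level that puts a control on folic acid is the level at which the protocol first calls for transfusion or an olaparib change because of anaemia. These are the outcomes the randomised part is meant to compare. By the time most of them can occur in a control, that control is due to start folic acid too.

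Two things are at stake. Section 8.1 hypothesises that replacing folic acid reduces transfusions and dose changes, so a null result here could be misread as folic acid not working. The comparator wording could also be read as an as-treated comparison, which would move switched controls, likely the most anaemic, out of their own arm.

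**Working it through.** **The plan's own figure.** Section 8.2 gives n=60 and N=75 for 66% against 50%, one-sided 0.05, 80% power. The formula [(1.645·√(0.5·0.5) + 0.842·√(0.66·0.34))/0.16]² gives 58.2, so 59. The exact binomial at n=60 (reject at 37 or more) has alpha 0.046 and power 0.802, and 60/0.80 = 75. The figures reproduce, but they size only the single-arm proportion. The plan gives no size, effect or event rate for the randomised comparison.

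**How many are randomised.** 66% of 60 to 75 patients is 39.6 to 49.5 folate-deficient. Suppose 37% to 100% of these also have Hgb in the entry window. This share is an assumption; the low end borrows the pooled anaemia frequency in the Background. Then 14.7 to 49.5 are randomised, about 7 to 25 per arm. The calculations below use 25, the favourable end.

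**Isolating the switch.** All rates are assumed. Let a be the risk of reaching Hgb below 10 (control a0, folic acid a1). Let t be the risk of transfusion once there (t0 without folic acid, t1 with it). Let s be the share of the later benefit that a switched control receives.

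- Control risk = a0·[(1−s)·t0 + s·t1]
- Folic acid risk = a1·t1
- Power = Φ{(d·√n − 1.96·√(2p̄(1−p̄))) / √(p1(1−p1) + p2(1−p2))}, two-sided 0.05

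First row: control 0.50·0.50 = 0.25; folic acid 0.25·0.25 = 0.0625; d = 0.1875; p̄ = 0.15625. Power = Φ{(0.1875·5 − 1.96·0.5135)/0.4961} = Φ(−0.139) = 0.44.

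| a0 / a1 | t0 / t1 | s | Control | Folic acid | Power, 25 per arm | n per arm, 80% |
|---|---|---|---|---|---|---|
| 50% / 25% | 50% / 25% | 0 | 25% | 6.25% | 44% | 58 |
| | | 0.5 | 18.75% | 6.25% | 26% | 109 |
| | | 1 | 12.5% | 6.25% | 11% | 341 |
| 40% / 20% | 50% / 25% | 0 | 20% | 5% | 36% | 76 |
| | | 0.5 | 15% | 5% | 21% | 141 |
| | | 1 | 10% | 5% | 10% | 435 |
| 50% / 25% | 50% / 50% | any | 25% | 12.5% | 20% | 152 |
| 50% / 50% | 50% / 25% | 0 | 25% | 12.5% | 20% | 152 |
| | | 0.5 | 18.75% | 12.5% | 9% | 529 |
| | | 1 | 12.5% | 12.5% | none | none |

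The switch costs information only if folic acid lowers transfusion risk below 10 g/dl; if it does not (t0 = t1), s has no effect. The difference is zero only if folic acid does nothing before 10 g/dl and switched controls get its full later benefit.

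**An outcome that is complete by the switch.** Reaching Hgb below 10, at 50% against 25%: Φ{(0.25·5 − 1.96·0.6847)/0.6614} = Φ(−0.139) = 0.44 at 25 per arm. That it equals the first row is a coincidence of the chosen rates. What matters is that it does not depend on s. These are normal approximations, and an exact test gives less: at 20 per arm the same rates give 37%, but 27% by Fisher's test.

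**The case against.** The strongest case against the point is that the overlap is incomplete and the comparison remains valid.

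No passage forbids transfusion above 10 g/dl; that it is absent there is inferred from Table 8. Olaparib changes are not tied to Hgb at all: Section 7.4.4 says "Any toxicity observed during the course of the study could be managed by interruption of the dose of study treatment or dose reductions", and Table 9 has, for other cytopenias, "Dose interruption until recovered to CTCAE gr 1 or better for a maximum of 4 weeks". A control below 10 g/dl with normal folate is not switched. Hgb level, serum folate and anaemia are already named outcomes. The study is a pilot, and these outcomes are secondary and unpowered.

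All of this stands, and it limits the point to most anaemia-driven events. Two replies remain. Controls are randomised for confirmed deficiency and left unsupplemented, so deficiency persisting at the crossing is plausible, though assumed. The named Hgb and anaemia outcomes have no time window, no summary measure and no rule for values after the switch. Patients also enter already below 12 g/dl, so the onset of anaemia cannot serve as the outcome.

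Two stronger readings are tempting. A reader might infer that the contrast has ended before the outcomes occur. The documents do not support that: patients reach 10 g/dl while treatments still differ, and a transfusion at the crossing reflects the assigned arm. A reader might also set power for Hgb below 10 beside power for transfusion and take the gap as the cost of the switch. If transfusion risk after crossing is equal in the two arms, both endpoints have the same risk ratio, and the gap reflects only that transfusion is rarer. Only a comparison of transfusion with and without the switch, as in the table, shows dilution.

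**Conclusion.** The point holds in limited form. Followed as written, the plan compares folic acid from randomisation with folic acid deferred until Hgb is below 10 g/dl with folate deficiency. For anaemia-driven transfusion and olaparib changes this is a valid but diluted contrast. It does not answer the question of folic acid against none, and the plan neither says so nor says how switches are handled.

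The size depends on assumed rates. In the main illustration the transfusion difference shrinks from 18.75 to 12.5 or 6.25 percentage points, and power falls as stated above. The dilution would be smaller if few controls are deficient at the crossing, and absent if folic acid has no effect below 10 g/dl. The primary endpoint, folate deficiency within three months, is not randomised and is untouched. This is a worthwhile, inexpensive correction to a secondary comparison, not a flaw that undermines the study.

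**What to change.** First reconcile Sections 1.1 and 3.1 with Section 8.4.1 on who is randomised. If grade 2 anaemia (Hgb 8 to below 10 g/dl) is included, time to Hgb below 10 is undefined for those patients, and Section 3.1 would give both arms folic acid at entry. This review does not say which boundary is right.

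Then, in Sections 2 and 8.4.1:

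1. Compare randomised patients by assigned arm, and replace the comparator wording based on receipt or need for this comparison.
2. Define the randomised anaemia endpoint as time from randomisation to first Hgb below 10 g/dl, or transfusion if earlier. Report Kaplan-Meier curves and a risk difference with 95% CI at a time point that follow-up supports. Section 3.4 ends the study 7 months from enrolment, so a patient randomised after month 4 has less than 3 months (7 − 4 = 3); censor such patients at their last count. Section 1.1, item 3, also mentions 12 months of two-weekly counts for patients needing replacement, so the follow-up horizon should be stated once.
3. Keep transfusion, interruption, reduction and discontinuation as supportive outcomes, labelled early versus deferred supplementation. Report the number and timing of switches.

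The rescue rule is unchanged. The two-weekly counts are already drawn, so no visits, samples or patients are added. The costs are a wording amendment to Section 2 and an endpoint that is mainly a laboratory event. The endpoint is not well powered at this size either, so the interval should carry the interpretation.
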